### **8.3 Exploratory Objectives**

- To measure the patient perceived burden by Patient-Reported Outcomes version of the Common Terminology Criteria for Adverse Events (PRO-CTCAE) in the subsequent TPC period
- To explore biomarkers based on availability of serum and tissue samples

## **9 INVESTIGATIONAL PLAN**

### **9.1 Overall Study Design and Plan**

This is a single-arm, open-label, multicenter, phase 2 study to evaluate the safety and efficacy of subsequent systemic TPC (commercially available) following first-line lenvatinib treatment for uHCC.

Approximately 100 subjects with uHCC will be enrolled to receive first-line treatment with lenvatinib in 28-day treatment cycles. Subjects with Child-Pugh A are eligible for this study.

Subjects will continue to receive lenvatinib treatment in continuous 28-day cycles until disease progression, development of unacceptable toxicity, subject request, withdrawal of consent, or study termination by the sponsor. Upon subject's completion of lenvatinib Off-Treatment Visit in first-line treatment of lenvatinib, subjects will be treated by commercially available, systemic TPC for uHCC in the subsequent TPC period.

The study will consist of Pretreatment Phase, Treatment Phase, and Post-Treatment Phase.

#### **9.1.1 Pretreatment Phase**

The pretreatment phase will last up to 21 days and will include Screening Period and a Baseline Visit/Period.

##### **9.1.1.1 Screening Period**

The Screening Period will last no longer than 21 days and will occur between Day -21 and Day -2. The purpose of the Screening Period is to obtain informed consent and establish protocol eligibility and disease characteristics. Informed consent will be obtained after the study has been fully explained to each subject and before the conduct of any screening procedures or assessments. Procedures to be followed when obtaining informed consent are detailed in [Section 5.3](#). Informed consent may be taken up to 4 weeks prior to Cycle 1 Day 1.

The Screening Disposition case report form (CRF) must be completed to indicate whether the subject is eligible to enroll in the study and to provide reasons for screen failure, if applicable.

Subjects must be screened within 21 days prior to the first dose of study treatment. The results of all screening assessments and evaluations must be completed and reviewed by the investigator prior to the Baseline Visit.

##### **9.1.1.2 Baseline Period/Visit**

Baseline assessments can be performed on Day -1 or prior to the start of study treatment on Cycle 1 Day 1. The purpose of the Baseline Visit is to confirm protocol eligibility and

disease characteristics, as specified in the inclusion/exclusion criteria (as detailed in [Section 9.3.1](#) and [Section 9.3.2](#)).

The screening assessment can serve as the baseline assessment, if performed within 72 hours before the first dose of study treatment. If the screening physical examination is performed  $>7$  days prior Cycle 1 Day 1, it must be repeated at the Baseline Visit. Laboratory tests and a pregnancy test (for female subjects of childbearing potential) may be performed up to 72 hours before the first dose of study treatment.

Subjects who complete the baseline assessment and meet the criteria for inclusion/exclusion ([Sections 9.3.1](#) and [9.3.2](#)) will begin the treatment phase. Results of baseline assessments must be obtained prior to the first dose of study treatment (Cycle 1 Day 1).

### 9.1.2 Treatment Phase

There will be 2 treatment periods in this study: Lenvatinib Treatment Period (Treatment Period 1) and the Subsequent TPC Treatment Period (Treatment Period 2).

#### 9.1.2.1 Lenvatinib Treatment Period (Treatment Period 1)

Lenvatinib Treatment Period for each subject will begin with the administration of first dose of lenvatinib on Cycle 1 Day 1 and will consist of administration of lenvatinib in 28-day treatment cycles. Treatment Period 1 will continue until completion of the lenvatinib Off-Treatment Visit that will occur within 30 days after the final administration of lenvatinib.

Lenvatinib treatment cycles will be counted continuously regardless of dose interruptions. Subjects will undergo safety and efficacy assessments as defined in the Schedule of Procedures/Assessments ([Table 3](#)). Subjects will continue to receive study treatment until disease progression, development of unacceptable toxicity, subject request, withdrawal of consent, or study termination by the sponsor.

Subjects will be permitted to continue lenvatinib treatment beyond mRECIST defined disease progression as long as the treating investigator considers that there is clinical benefit and, the subject is tolerating study treatment. The assessment of clinical benefit should take into account whether the subject is clinically deteriorating and unlikely to receive further benefit from continued treatment. All decisions to continue treatment beyond initial progression must be discussed with the Eisai Medical Monitor. Subjects will discontinue study treatment upon evidence of further progression and/or loss of clinical benefit, as judged by the investigator.

#### 9.1.2.2 Subsequent Treatment Period (TPC Period, Treatment Period 2)

The subsequent TPC period will begin upon the completion of the lenvatinib Off-Treatment Visit in first-line treatment of lenvatinib. Subjects will be treated with commercially available systemic TPC for uHCC. The first treatment of a single agent or combination of multiple drugs after lenvatinib treatment will be considered as the subsequent TPC. Locoregional therapies (ie, chemoembolization/radioembolization, etc) procedures will not

be considered as a second line treatment following lenvatinib. If the investigator deems a subject inappropriate for commercially available systemic TPC as the subsequent treatment following lenvatinib, subjects will be followed in the survival Follow-Up period. All treatment following lenvatinib will be captured in the case report form. Data will be collected from the start of TPC, then at intervals as indicated in Schedule of Procedures/Assessments ([Table 3](#)).

Subjects starting subsequent TPC  $\geq$ 8 weeks after lenvatinib off-treatment visit may be considered after discussion with sponsor.

#### 9.1.2.3 Follow-Up Period (Survival Follow-Up)

The Follow-Up Period will begin immediately after the final visit of the subsequent TPC period (Treatment Period 2). Subjects will be followed every 12 weeks for survival and will continue as long as the study subject is alive or the subject withdraws consent. If the investigator deems a subject inappropriate for commercially available subsequent systemic TPC, the subject will be followed for survival every 12 weeks after the lenvatinib Off-Treatment Visit of the Lenvatinib Treatment Period (Treatment Period 1). Subjects' survival status and all additional anticancer treatments received will be recorded.

The sponsor may decide to terminate survival follow-up of subjects after the completion of the primary analysis or when all subjects have discontinued study treatment.

## 9.2 Discussion of Study Design, Including Choice of Control Groups

This open-label, multicenter, phase 2 study will employ a single-arm design to evaluate the safety and efficacy of subsequent systemic TPC (commercially available) following first-line lenvatinib treatment of uHCC, and to gain more understanding of the safety and efficacy of other systemic anti-HCC therapy following lenvatinib treatment.

## 9.3 Selection of Study Population

Approximately 100 subjects with uHCC are planned to be enrolled at approximately 20 to 25 sites in the US and Canada. Subjects who do not meet all of the inclusion criteria or who meet any of the exclusion criteria will not be eligible to receive study drug.

### 9.3.1 Inclusion Criteria

Subjects must meet all of the following criteria to be included in this study:

1. Subjects must have confirmed diagnosis of uHCC with any of the following criteria:
  - a. Histologically or cytologically confirmed diagnosis of HCC
  - b. Clinically confirmed diagnosis of HCC according to American Association for the Study of Liver Diseases (AASLD) criteria, including cirrhosis of any etiology or with chronic hepatitis B or C infection criteria
2. At least one measurable target lesion regardless if hepatic or non-hepatic according to

mRECIST meeting the following criteria:

a. Hepatic lesion

- The lesion can be accurately measured in at least one dimension as  $\geq 1.0$  cm (viable tumor for typical; and longest diameter for atypical), and
- The lesion is suitable for repeat measurement,

b. Nonhepatic lesion

- Lymph node lesion that measures at least one dimension as  $\geq 1.5$  cm in the short axis
- Non-nodal lesion that measures  $\geq 1.0$  cm in the longest diameter

Lesions previously treated with radiotherapy or locoregional therapy must show radiographic evidence of disease progression to be deemed a target lesion.

3. Subjects categorized on the Barcelona Clinic Liver Cancer (BCLC) staging system to Stage B (not applicable for transarterial chemoembolization [TACE]) or Stage C
4. Adequate bone marrow function, defined as:
  - Absolute neutrophil count (ANC)  $\geq 1.5 \times 10^9/L$
  - Hemoglobin  $\geq 8.5$  g/dL
  - Platelet count  $\geq 75 \times 10^9/L$
5. Adequate liver function, defined as:
  - Albumin  $\geq 2.8$  g/dL
  - Bilirubin  $\leq 3.0$  mg/dL
  - Aspartate aminotransferase (AST), alkaline phosphatase (ALP), and alanine aminotransferase (ALT)  $\leq 5 \times$  the upper limit of normal (ULN)
6. Adequate blood coagulation function, defined as international normalized ratio (INR)  $\leq 2.3$
7. Adequate renal function defined as creatinine clearance  $>30$  mL/min calculated per the Cockcroft and Gault formula
8. Adequate pancreatic function, defined as lipase  $\leq 1.5 \times$  ULN
9. Adequately controlled blood pressure (BP) with up to 3 antihypertensive agents, defined as BP  $\leq 150/90$  mmHg at Screening and no change in antihypertensive therapy within 1 week prior to Cycle 1/Day 1
10. Child-Pugh A
11. Eastern Cooperative Oncology Group Performance Status (ECOG PS) 0 or 1
12. Survival expectation of 12 weeks or longer before starting study drug
13. Males or females aged at least 18 years at the time of informed consent
14. Provide written informed consent
15. Willing and able to comply with all aspects of the protocol

### 9.3.2 Exclusion Criteria

Subjects who meet any of the following criteria will be excluded from this study:

1. Imaging findings for HCC corresponding to any of the following:
  - a. HCC with  $\geq 50\%$  liver occupation
  - b. Clear invasion into the bile duct
  - c. Portal vein invasion at the main portal branch (Vp4)
2. Subjects who have received any systemic chemotherapy, including sorafenib, regorafenib or other anti-vascular endothelial growth factor (VEGF) therapy, nivolumab, or any systemic investigational anticancer agents, including lenvatinib, for advanced/uHCC.  
Note: Subjects who have received local hepatic injection chemotherapy (if not within 28 days prior to the first dose of lenvatinib study treatment ) are eligible
3. Subjects who have received any anticancer therapy (including surgery, percutaneous ethanol injection, radio frequency ablation, transarterial [chemo] embolization, hepatic intra-arterial chemotherapy, biological, immunotherapy, hormonal, or radiotherapy) or any blood enhancing treatment (including blood transfusion, blood products, or agents that stimulate blood cell production, eg, granulocyte colony-stimulating factor [G-CSF]) within 28 days prior to the first dose of lenvatinib study treatment.
4. Subjects who have not recovered from toxicities as a result of prior anticancer therapy such as the local hepatic injection chemotherapy or any prior therapy for other cancer types. Recovery is defined as <Grade 2 severity per Common Terminology Criteria for Adverse Events Version 4.03 (CTCAE v4.03), except alopecia and infertility
5. Significant cardiovascular impairment within 6 months of the first dose of study drug: history of congestive heart failure greater than New York Heart Association (NYHA) Class II, unstable angina, myocardial infarction or stroke, cardiac arrhythmia associated with hemodynamic instability, or a left ventricular ejection fraction (LVEF) below the institutional normal range as determined by multigated acquisition (MUGA) scan or echocardiogram
6. Prolongation of QTcF (QT interval corrected for heart rate using Fridericia's correction) interval to  $>480$  ms
7. Gastrointestinal malabsorption or any other condition that might affect the absorption of lenvatinib in the opinion of the investigator
8. Bleeding or thrombotic disorders or use of anticoagulants such as, warfarin or similar agents requiring therapeutic INR monitoring (Treatment with low molecular weight heparin is allowed)
9. Gastrointestinal bleeding event or active hemoptysis (bright red blood of at least half teaspoon) within 28 days prior to the first dose of lenvatinib study treatment
10. Gastric or esophageal varices that require treatment
11. Active malignancy (except for HCC or definitively treated melanoma in-situ, basal or squamous cell carcinoma of the skin, or carcinoma in-situ of the cervix) within the past 36 months
12. Any history of, or current brain or subdural metastases
13. Subjects having  $>1+$  proteinuria on urine dipstick testing will undergo 24-hour urine collection for quantitative assessment of proteinuria. Subjects with urine protein  $\geq 1$  g/24 h will be ineligible.

14. Arterial-portal venous shunt or arterial-venous shunt preventing proper diagnosis of tumor
15. Any medical or other condition that in the opinion of the investigator would preclude the subject's participation in a clinical study
16. Known intolerance to lenvatinib or any of the excipients
17. Human immunodeficiency virus (HIV) positive or active infection requiring treatment (except for hepatitis virus)
18. Any history of drug or alcohol dependency or abuse within the prior 2 years
19. Any subject who cannot be evaluated by either triphasic liver computed tomography (CT) or triphasic liver magnetic resonance imaging (MRI) because of allergy or other contraindication to both CT and MRI contrast agents
20. Major surgery within 3 weeks prior to the first dose of lenvatinib study treatment or scheduled for surgery during the study
21. Subject has had a liver transplant
22. Females who are breastfeeding or pregnant at Screening or Baseline (as documented by a positive beta-human chorionic gonadotropin [ $\beta$ -hCG] (or human chorionic gonadotropin [hCG]) test with a minimum sensitivity of 25 IU/L or equivalent units of  $\beta$ -hCG [or hCG]). A separate baseline assessment is required if a negative screening pregnancy test was obtained more than 72 hours before the first dose of study drug.
23. Females of childbearing potential who:
  - Within 28 days before study entry, did not use a highly effective method of contraception, which includes any of the following:
    - total abstinence (if it is their preferred and usual lifestyle)
    - an intrauterine device or intrauterine hormone-releasing system (IUS)
    - a contraceptive implant
    - an oral contraceptive (with additional barrier method) (Subject must be on a stable dose of the same oral contraceptive product for at least 28 days before dosing and throughout the study and for 28 days after study drug discontinuation.)
    - have a vasectomized partner with confirmed azoospermia.
  - Do not agree to use a highly effective method of contraception (as described above) throughout the entire study period and for 28 days after study drug discontinuation.

For sites outside of the EU, it is permissible that if a highly effective method of contraception is not appropriate or acceptable to the subject, then the subject must agree to use a medically acceptable method of contraception, ie, double-barrier methods of contraception such as latex or synthetic condom plus diaphragm or cervical/vault cap with spermicide.

All females will be considered to be of childbearing potential unless they are postmenopausal (amenorrheic for at least 12 consecutive months, in the appropriate age group, and without other known or suspected cause) or have been sterilized surgically (ie, bilateral tubal ligation, total hysterectomy, or bilateral oophorectomy, all with surgery at least 1 month before dosing).

24. Males who have not had a successful vasectomy (confirmed azoospermia) or they and their female partners do not meet the criteria above (ie, not of childbearing potential or practicing highly effective contraception throughout the study period and for 96 days after study drug discontinuation). No sperm donation is allowed during the study period and for 96 days after study drug discontinuation.

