#### 9.5.4.2 Reporting of Pregnancy and Exposure to Study Drug Through Breastfeeding

Any pregnancy in a female subject (or partner of a male subject) in which the estimated date of conception is either before the last visit or within 30 days of last dose of study treatment, or any exposure to study drug through breastfeeding during study treatment or within 30 days of last dose of study treatment, must be reported.

If an adverse outcome of a pregnancy is suspected to be related to study drug exposure, this should be reported regardless of the length of time that has passed since the exposure to study treatment.

A congenital anomaly, death during perinatal period, an induced abortion, or a spontaneous abortion are considered to be an SAE and should be reported in the same time frame and in the same format as all other SAEs (see [Section 9.5.4.1](#)).

Pregnancies or exposure to study drug through breastfeeding must be reported by fax or email as soon as possible but no later than 1 business day from the date the investigator becomes aware of the pregnancy. The contact information for the reporting of pregnancies and exposure to study drug through breastfeeding is provided in the Investigator Study File. The Pregnancy Report Form must be used for reporting. All pregnancies must be followed to outcome. The outcome of the pregnancy must be reported as soon as possible but no later than 1 business day from the date the investigator becomes aware of the outcome.

A subject who becomes pregnant must be withdrawn from the study.

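### Exclusion 24 joins its two conditions with 'or', so as written it bars every man without a confirmed-azoospermic vasectomy, even when he and his partner meet the contraception criteria

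*Combined protocol and SAP*

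**What the plan says.** Section 9.3.2 opens its list with "Subjects who meet any of the following criteria will be excluded from this study", and Section 9.3 repeats the rule for subjects "who meet any of the exclusion criteria will not be eligible to receive study drug". One exclusion is therefore enough to bar a subject.

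Criterion 24 excludes "Males who have not had a successful vasectomy (confirmed azoospermia) or they and their female partners do not meet the criteria above". A parenthesis explains that meeting the criteria means the partner is "not of childbearing potential or practicing highly effective contraception throughout the study period and for 96 days after study drug discontinuation". The criterion then adds: "No sperm donation is allowed during the study period and for 96 days after study drug discontinuation". The synopsis carries the same wording with the same connective.

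Three other places bear on how criterion 24 should be read:

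- Criterion 23, to which 'the criteria above' points, includes a vasectomised partner with confirmed azoospermia in its list of highly effective methods.
- Inclusion 13 in Section 9.3.1 admits "Males or females aged at least 18 years at the time of informed consent" and sets no vasectomy condition.
- Section 9.5.4.2 makes reportable "Any pregnancy in a female subject (or partner of a male subject"), within stated time limits.

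Nothing in the current text corrects or qualifies the connective, and none of the three logged amendments records a change to criterion 24.

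**The concern.** The sentence has two negative conditions, each with its own subject and verb: the man has not had a successful vasectomy; he and his partner do not meet the criteria. Joined by 'or' inside an exclusion, either one excludes. A man without a vasectomy whose partner is postmenopausal, or who with his partner uses a listed method, meets the first condition and is formally ineligible.

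This is an operative eligibility rule. Section 11.2 requires conduct in strict accordance with the protocol, and Section 9.1.1.1 requires each site to record eligibility and any reason for screen failure. A site that follows the sentence literally turns away men whom the rest of the protocol expects to enrol. A site that reads through to the evident intent enrols them against the written criterion. Different sites could resolve this differently in a study of about 100 subjects.

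**Working it through.** The plan gives no figure on this point, so the check is one of logic. Let V mean a successful vasectomy with confirmed azoospermia, and C mean that the man and his partner meet the criteria above.

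- As written: exclude if (not V) or (not C).
- Form suggested by the rest of the document: exclude if (not V) and (not C).

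**Step 1: which combinations can occur.** Two yes/no conditions give four combinations. Because criterion 23 lists the partner's confirmed-azoospermic vasectomy as a highly effective method, a couple relying on V is already practising a listed method. V therefore implies C, and the combination 'V, not C' is essentially empty. Three remain.

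| Man | As written ('or') | With 'and' |
|---|---|---|
| V (hence C) | eligible | eligible |
| not V, C | **excluded** | eligible |
| not V, not C | excluded | excluded |

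**Step 2: where the readings differ.** They differ in one case only: no vasectomy, contraception criteria met. Those are the men for whom the parenthesis about partner status and the 96-day period was written.

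**Step 3: what each reading leaves of the sentence.** Since V implies C, every man caught by 'not C' is already caught by 'not V'. Under 'or' the rule collapses to 'no vasectomy, no entry', and deleting the second condition would change nothing. Under 'and' both conditions have work to do.

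**Step 4: comparison with the rest of the protocol.**

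- Inclusion 13 admits men without a vasectomy requirement, whereas the literal criterion 24 imposes one.
- The ban on sperm donation has little purpose if every enrolled man is azoospermic.
- Reporting of partner pregnancies fits the enrolment of fertile men. It is weaker evidence, since it would also cover a failed vasectomy.

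**Step 5: effect on the statistics.** The half-widths in Section 9.7.2, Table 4, depend on the number of subjects reaching TPC and the assumed 75% rate of Grade 3 or higher events, not on criterion 24. Section 9.7.1.2 defines the Safety Analysis Set by receipt of at least one dose and defines no per-protocol set, so a man enrolled against the literal wording stays in the analysis.

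**The case against.** The strongest reply is that no sensible investigator would read the sentence literally. A reading that empties half the criterion is not the natural one, and the ordinary sense is a man who has neither a vasectomy nor a couple meeting the contraception criteria. The same text that proves the intent to a reviewer is in front of the sites. The sponsor has also used an amendment to clear up eligibility wording before (Amendment 02, on the non-hepatic lesion criterion), and criterion 24 was left alone.

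Much of this stands. The intent is recoverable, and nothing in the documents shows that any site applied the literal rule. The absence of an amendment, however, does not show that no site was confused. The reply also concedes that investigators must override the written criterion to apply it as meant, which sits badly with Section 11.2.

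Three stronger readings are tempting, and the documents do not support them:

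- A reader might infer that the second condition also removes a vasectomised man whose partner uses no other method. It does not, because criterion 23 counts his vasectomy as a qualifying method.
- A reader might try to put a number on the men lost or on the deviations created. The documents give neither the expected share of men nor the share with a confirmed-azoospermic vasectomy. Any count would also assume that every site reads the text literally.
- A reader might infer that the sponsor meant to require vasectomy. The alternative spelled out in the criterion itself, together with inclusion 13, points the other way.

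**Conclusion.** The point holds as a drafting error in an operative eligibility rule, present in both the synopsis and Section 9.3.2. As written, the rule excludes every man without a confirmed-azoospermic vasectomy, including those who meet the contraception criteria with their partners. That contradicts the criterion's own alternative and other parts of the protocol.

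The consequence is a risk of uneven screening between sites and of formal eligibility deviations. Its size cannot be stated from the documents. The conclusion rests on the grammar of the sentence, on the rule that any one exclusion disqualifies, and on criterion 23 making a vasectomised man's couple compliant. It does not rest on any assumption about how sites behaved. No sample-size figure, analysis set or planned analysis is affected, and the evident intent limits the practical harm. It is worth correcting because the correction is so small.

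**What to change.** Reconcile the connective in criterion 24 with the rest of the document, in the synopsis and in Section 9.3.2 together. The form consistent with the other passages replaces 'or' with 'and', so that the criterion excludes only men who have neither a successful vasectomy nor a couple meeting the criteria. The sponsor should confirm that this is what it intends. The contraceptive methods, the 96-day period and the sperm-donation sentence stay as they are.

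The cost is one connective in two places, carried in the next amendment under Section 11.1, with no new procedures or data. When the change is made, the sponsor can check the screen-failure reasons already collected on the Screening Disposition form to see whether any man was turned away on this criterion alone. That would give the size that the documents cannot.
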